#### **4.5.2. Adverse Events**

The verbatim terms used in the CRF by investigators to identify adverse events will be coded using the MedDRA. In general, any AE occurring at or after the initial administration of study intervention up to 4 weeks after the last dose or treatment discontinuation is considered to be treatment emergent. If the event occurs on the day of the initial administration of study intervention, and either event time or time of administration are missing, then the event will be assumed to be treatment emergent. If the event date is recorded as partial or completely missing, then the event will be considered to be treatment emergent unless it is known to be prior to the first administration of study intervention based on partial onset date or resolution date. All reported treatment-emergent adverse events will be included in the analysis. For each adverse event, the

number and percentage of participants who experience at least 1 occurrence of the given event will be summarized by intervention group. The overall AEs will also be summarized by age group (adult, adolescent) and intervention group.

Summary tables will be provided for treatment-emergent adverse events:

- AEs
- Serious AEs (SAEs)
- AEs of Special Interest (AESIs)
- AEs leading to discontinuation of study intervention
- AEs of severe intensity
- AEs related to study intervention.
- AE of psoriasis

In addition to the summary tables, listings will be provided for participants who:

- Had SAEs
- Had AESIs
- Had AEs leading to discontinuation of study intervention
- Had AEs of severe intensity
- Had AE of psoriasis
- Had suicidal ideation or suicidal behavior
- Had serious hypersensitivity including anaphylactic reactions

A listing of participants who died will be provided.

Since safety should be assessed relative to follow-up, most AE summary tables will include average weeks of follow-up for each intervention group.

An AESI, which may be serious or non-serious, is an AE of scientific and medical concern specific to the sponsor's product or program, for which ongoing monitoring and expedited communication (within 24 hours) by the investigator to the sponsor is warranted. The AESIs for JNJ-77242113 are active TB, malignancy, and possible Hy's law cases.

A **possible Hy's law case** is defined by the occurrence of ALT/AST  $\geq 3 \times \text{ULN}$ , together with Tbili  $\geq 2 \times \text{ULN}$  or INR  $> 1.5$  (if measured).

Psoriasis rebound will be assessed during the withdrawal period for adult participants who were randomized to placebo at Week 24 and withdrawn from JNJ-77242113. Psoriasis rebound is defined as an event of new erythrodermic or pustular psoriasis, or a PASI of  $\geq 125\%$  of the baseline PASI (ie, a worsening of PASI by 25% or greater from baseline) that occurred within 3 months

during the withdrawal period from the time participants were withdrawn from JNJ-77242113 at Week 24.

Adjudicated results for events such as Cardiovascular events, TB and Opportunistic Infections will be summarized.

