7. DISCONTINUATION OF STUDY INTERVENTION AND PARTICIPANT DISCONTINUATION

7.1. Discontinuation of Study Intervention

If a participant discontinues study intervention for any reason before the end of the study, then the Early Termination Visit assessments must be obtained (Section 1.3.2). Study intervention assigned to the participant who discontinued study intervention may not be assigned to another participant (Section 6.2). Additional participants will not be entered in this study. Participants who discontinue

study intervention but do not terminate study participation will continue to return for protocol-specified procedures and evaluations. Discontinuation from study intervention does not mean that the participant is required to withdraw informed consent and leave the study.

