8.4. Adverse Events, Serious Adverse Events, and Other Safety Reporting

Timely, accurate, and complete reporting and analysis of safety information, including AEs, serious AEs, and PQCs, from clinical studies are crucial for the protection of participants, investigators, and the sponsor, and are mandated by regulatory agencies worldwide. The sponsor has established Standard Operating Procedures in conformity with regulatory requirements worldwide to ensure appropriate reporting of safety information; all clinical studies conducted by the sponsor, or its affiliates will be conducted in accordance with those procedures.

Adverse events will be reported by the participant (or, when appropriate, by a caregiver, surrogate, or the participant's legally acceptable representative in case of adolescents, where applicable) for the duration of the study.

Further details on AEs, SAEs, and PQCs can be found in [Appendix 3](#). Adverse Events, Serious Adverse Events, Product Quality Complaints, and Other Safety Reporting: Definitions and Procedures for Recording, Evaluating, Follow-up, and Reporting.

8.4.1. Time Period and Frequency for Collecting Adverse Event and Serious Adverse Event Information

All Adverse Events

All AEs and special reporting situations, whether serious or non-serious, will be reported from the time a signed and dated ICF is obtained until completion of the participant's last study-related procedure, which may include contact for follow-up of safety.

All AEs with an onset date after the signing of the ICF and up to 4 weeks after study treatment discontinuation must be recorded on specific AE pages of the eCRF.

Serious Adverse Events

All SAEs occurring during the study must be reported to the appropriate sponsor contact person by study site personnel immediately but no later than 24 hours of their knowledge of the event.

Serious adverse events, including those spontaneously reported to the investigator within 4 weeks after the last dose of study intervention, must be reported. The sponsor will evaluate any safety information that is spontaneously reported by an investigator beyond the time frame specified in the protocol.

All SAEs occurring after signature of the ICF up to 4 weeks after study treatment discontinuation must be recorded on AE pages in the eCRF and on an SAE form, regardless of the investigator-attributed causal relationship with study treatment or study mandated procedures.

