8.4.6. Adverse Events of Special Interest

An AESI, which may be serious or non-serious, is an AE of scientific and medical concern specific to the sponsor's product or program, for which ongoing monitoring and expedited communication (within 24 hours) by the investigator to the sponsor is warranted. The AESIs for JNJ-77242113 are active TB, malignancy, and possible Hy's Law cases.

A **possible Hy's law case** is defined by the occurrence of ALT/AST $\geq 3 \times \text{ULN}$, together with Tbili $\geq 2 \times \text{ULN}$ or INR > 1.5 (if measured). Any possible Hy's Law case is considered a medically important event and must be reported to the sponsor in an expedited manner using the AESI form, even before all other possible causes of liver injury have been excluded ([FDA 2009](#)).

Any newly identified malignancy or case of active TB occurring after the first administration of study intervention must be reported by the investigator according to the procedures in [Appendix 3](#). Investigators are also advised that active TB is considered a reportable disease in most countries/territories. An AESI is considered serious only if it meets the definition of an SAE.

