##### **Summary through Week 52 and /or through the reporting period (approximately the date when last participant finishing Week 52 visit):**

Safety data will be summarized by intervention group defined as follows:

- Placebo → JNJ-77242113: all participants who were randomized to placebo at Week 0, and later crossed over to receive treatment with JNJ-77242113 at or after Week 16. Only the safety events/measurements from these participants that occurred at or after Week 16 will be included.
- JNJ-77242113: Participants who were randomized to JNJ-77242113 at Week 0 and were treated with JNJ-77242113. All the safety events/measurements from these participants that occurred at or after Week 0 administration will be included in this group. However, safety events that occurred during the withdrawal period (on and after Week 28 and before retreatment) may be excluded for participants who were rerandomized to placebo at Week 24.
- Combined JNJ-77242113: all participant as described above in the Placebo → JNJ-77242113 and the JNJ-77242113 groups.

In addition, selected safety analysis from Week 24 through Week 52 may be performed among participants who were randomized to either receive placebo or continue to receive JNJ-77242113 at Week 24.

- Placebo (withdrawal): Participants who were randomized to JNJ-77242113 at Week 0, were PASI 75 or IGA 0 or 1 responders at Week 24, and rerandomized to placebo group at Week 24. Only the safety events/measurements from these participants that occurred at or after Week 24 randomization and before retreatment with JNJ-77242113 will be included in this group.
- Placebo → retreatment: Participants who were randomized to placebo at Week 24, started treatment with placebo, and retreated with JNJ-77242113 upon loss of 50% Week 24 PASI improvement. Only the safety events that occurred at or after their first retreatment of JNJ-77242113 will be included in this group.
- Placebo (combined 1 and 2 above): Participants who were randomized to placebo at Week 24. All safety events/measurements from these participants that occurred at or after Week 24 randomization will be included.
- JNJ-77242113 (Rerandomization): Participants who were randomized to JNJ-77242113 at Week 24 and continue to receive treatment with JNJ-77242113. All safety events occurred at or after Week 24 rerandomization will be included in this group.

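### The SAP's AESI table omits malignancy and active TB found more than 4 weeks after stopping study intervention, and no required table is assured to count such cases during the withdrawal period

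*SAP*

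**What the plan says.** **Analysis.** SAP 4.5.2 defines an event from the initial administration "up to 4 weeks after the last dose or treatment discontinuation is considered to be treatment emergent". It continues: "Summary tables will be provided for treatment-emergent adverse events", and AESIs are on the list that follows. The same section states: "The AESIs for JNJ-77242113 are active TB, malignancy, and possible Hy's law cases". The definition opens with a general qualifier, but no exception is written for any AESI.

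**Reporting and follow-up.** Protocol 8.4.6: "Any newly identified malignancy or case of active TB occurring after the first administration of study intervention must be reported by the investigator". No end date is given. Protocol 7.1 says that participants who discontinue "study intervention but do not terminate study participation will continue to return for protocol-specified procedures and evaluations". Completion is defined by the Week 160 assessments (protocol 4.4), and the Schedule of Activities has adverse events and TB evaluation at every visit.

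**Recording.** Protocol 8.4.1 gives two end points. All AEs are to be reported "until completion of the participant's last study-related procedure, which may include contact for follow-up of safety", but those with onset "up to 4 weeks after study treatment discontinuation must be recorded on specific AE pages of the eCRF". The eCRF limit for SAEs is also 4 weeks.

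**Withdrawal period.** In the Week 52 summary for the JNJ-77242113 group, SAP 4.5 says that "safety events that occurred during the withdrawal period (on and after Week 28 and before retreatment) may be excluded" for participants re-randomized to placebo at Week 24.

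**The concern.** Malignancy and active TB are two of the three events that the sponsor singled out for special monitoring. The protocol treats them as reportable whenever they occur after first dose, and it keeps looking for them in people who have stopped study intervention. The SAP then applies to them the same 4-week cut-off as to every other event. A case can be found at a scheduled visit and reported as required, and still be missing from the only planned summary table of AESIs.

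At stake is the completeness of a small count. A table with few expected cases is sensitive to the omission of any one. The denominator is also unclear: SAP 4.5.2 says that most AE tables will show average weeks of follow-up, but not whether that follow-up stops at the same 4 weeks. If it does not, events are cut off while follow-up time continues, and the apparent rate falls.

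**Working it through.** The plan states no figure to reproduce, so the check is mainly of text.

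**1. Definitions side by side.**
- Protocol 9.3.5: treatment-emergent from the initial administration onward, with no upper limit.
- SAP 4.5.2: the same start, ending 4 weeks after last dose or discontinuation.
- The SAP's summary of changes says that the window was added in Amendment 1 and calls it a clarification. No reason is given for applying it to malignancy and TB.

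The SAP is narrower than the protocol on the events that enter the AESI table.

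**2. Who is affected by the 4-week rule, and for how long.** It affects participants who stop study intervention and stay in the study. With follow-up to Week 160:

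uncounted weeks = 160 − (stop week + 4)

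- Stop at Week 16: 160 − 20 = 140
- Stop at Week 24: 160 − 28 = 132
- Stop at Week 52: 160 − 56 = 104
- Stop at Week 100: 160 − 104 = 56
- Treatment completed at Week 156: 160 − 160 = 0

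Completers, and those who leave the study by 4 weeks after their last dose, lose nothing.

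**3. How many cases.** The documents give neither the share who stop and stay nor an event rate. The following ranges are assumptions for illustration only: 2% to 10% of 600 stop and stay, mean stop week 16 to 100, and 0.2 to 1.0 malignancies per 100 person-years.

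Person-years = 600 × share × uncounted weeks / 52.18

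- Low: 600 × 0.02 × 56 / 52.18 = 12.9 person-years; × 0.2/100 = 0.03 cases
- High: 600 × 0.10 × 140 / 52.18 = 161.0 person-years; × 1.0/100 = 1.6 cases

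The base of 600 includes participants starting on placebo, some of whom could stop before taking JNJ-77242113, so it is generous.

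**4. Where a late case could still appear.** The AESI listing in SAP 4.5.2 is not expressly limited to treatment-emergent events. Adjudicated TB results are to be summarized with no window stated. Malignancy is not named in that sentence.

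**5. Withdrawal period.** This is a separate rule. The optional exclusion starts at Week 28, which is 24 + 4: the same 4-week convention counted from the last JNJ-77242113 dose. The alternative columns for Weeks 24 to 52 (withdrawal, retreatment and combined placebo groups) would count these events, but SAP 4.5 describes them as selected analyses that may be done. The Week 160 summary is a single line about exposure to JNJ-77242113 and does not mention withdrawal-period events. So no required table is assured to count a malignancy or TB case arising then, after 24 weeks of JNJ-77242113.

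**6. Recording.** Appendix 3 (10.3.1) sends the reader to 8.4.1 for the time of last AE recording, where two answers stand. Appendix 3 (10.3.5) says that all AEs go in the CRF, with no time limit in that sentence. A site cannot tell from the text whether a malignancy found 10 weeks after discontinuation must be entered.

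**The case against.** The strongest case for the plan is that a treatment-emergent window is an attribution convention, and 4 weeks is generous. With the half-life of 9 to 12 hours in protocol 2.2, 4 weeks (672 hours) is at least 672 / 12 = 56 half-lives. Protocol 8.4.6 is a reporting duty on investigators, not a rule about tables. The 8.4.1 wording says what must be recorded up to 4 weeks and does not bar later entries. Late cases may also be listed. All of this stands. It is a good reason to keep the 4-week table, but it does not make that table sufficient for two events which the protocol follows without an end date. A listing gives no incidence or comparison.

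Three stronger readings are tempting, and the documents do not support them.

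- A reader might infer that a cancer at Week 40 in someone re-randomized to placebo at Week 24 misses the eCRF. That person is still taking blinded placebo, which the protocol classes as investigational product (6.1). If they remain on it, study treatment has not been discontinued and the 4-week recording limit has not started.
- A reader might size the loss as 135 × (52 − 28) = 3,240 person-weeks, or 15.6% of 400 × 52 = 20,800. That measures the optional exclusion in SAP 4.5, not the 4-week rule. Nor is it an upper bound. The 135 is 75% PASI 75 responders among 540 × 2/3 = 360 adults, halved, whereas PASI 75 or IGA 0/1 responders are re-randomized, so an arm could reach 360 / 2 = 180. Retreatment would shorten the time. The percentage should not be used.
- A reader might infer that a missing case would change the safety conclusion. SAP 4.5 plans no formal safety comparison, and the documents set no AESI threshold.

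**Conclusion.** The point holds in a limited form. For participants who stop study intervention and remain in scheduled visits, malignancy and active TB found more than 4 weeks later are left out of the AESI summary table. That table is narrower than the protocol's own definition of treatment emergence and its reporting duty. The uncounted stretch is 140 weeks for a stop at Week 16 and 104 weeks for a stop at Week 52, assuming that the participant stays to Week 160. For the group re-randomized to placebo, cases are not removed by rule; the exclusion and the tables that would offset it are both optional, so counting is not assured.

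The number of cases cannot be derived from the documents and is probably small. The illustrative 0.03 to 1.6 rests wholly on assumed rates. This is a gap in completeness that is cheap to close; a distorted result has not been shown.

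**What to change.** **SAP 4.5 and 4.5.2.** Add one table of all malignancy and active TB cases from the first JNJ-77242113 dose to the last study contact, including the withdrawal period, with follow-up time over the same interval as the denominator. Present it beside the 4-week treatment-emergent table, which stays as it is.

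**Protocol 8.4.1.** Reconcile the two end points (last study-related procedure, and 4 weeks after discontinuation) with 8.4.6 and Appendix 3, so that it is clear that late AESIs are recorded on the eCRF.

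**Cost.** One extra table and clarified wording. Visits and adverse event questioning already take place, so no procedure is added. The reported AESI count may be slightly higher.

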### 4.5.3. Additional Safety Assessments

#### 4.5.3.1. Clinical Laboratory Tests

Clinical laboratory tests will be displayed for the participants included in the safety analysis set.

Box plots of laboratory measurements and change from baseline will be provided for the select laboratory measurements. In addition, box plot for select laboratory measurements may be provided among adolescent participants.

Applicable laboratory results will be graded according to National Cancer Institute's Common Terminology Criteria for Adverse Events (NCI-CTCAE). The proportion of participants with post-baseline values by maximum toxicity grade for clinical laboratory tests will be summarized overall and by age group. Participants with toxicity grades  $\geq 2$  will be listed.

In addition, for selected laboratory parameters (i.e. ALT, AST), ULN will also be used to identify abnormal laboratory test results. Lipid and hs-CRP will be summarized. The 4-week window after the last dose or treatment discontinuation will be applied.

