
14. Topical medications/treatments that could affect psoriasis evaluations including, but not limited to:
 
 Corticosteroids, calcineurin inhibitors, vitamin D analogs, vitamin A analogs, retinoids, tar, anthralin, calcipotriene, tazarotene, methoxsalen, trimethylpsoralens, fumarate, PDE4 inhibitors, aryl hydrocarbon receptor-modulating agents Shampoos that contain corticosteroids, coal tar, or vitamin D3 analogs Herbal treatments or traditional Taiwanese, Korean, or Chinese medicines 	
2 weeks prior to the first administration of study intervention

15. Live virus or bacterial vaccination
	
4 weeks (or longer if required per vaccine package insert) prior to the first administration of study intervention

16. BCG vaccination
	
1 year prior to the first administration of study intervention

Diagnostic Assessments

17. Screening laboratory test results within the following parameters:
- Hemoglobin: <10 g/dL (SI: <100 g/L)
 - White blood cells: <3.5 x 10³/μL (SI: <3.5 GI/L)

- Neutrophils: $<1.5 \times 10^3/\mu\text{L}$ (SI: $<1.5 \text{ GI/L}$)
- Platelets: $<100 \times 10^3/\mu\text{L}$ (SI: $<100 \text{ GI/L}$)
- eGFR: $<60 \text{ mL/min/1.73 m}^2$
- Aspartate aminotransferase: $>2 \times \text{ULN}$
- Alanine aminotransferase: $>2 \times \text{ULN}$

If one or more of the laboratory parameters is out of range, a single retest of laboratory values is permitted during the screening period.

18. Test positive for the following infections at screening:
 - a. HBV ([Appendix 7](#))
 - b. Hepatitis C (seropositive for antibodies and positive confirmatory test for HCV, ie, HCV PCR [[Appendix 7](#)])
 - c. HIV
19. Has a chest radiograph (or CT scan) within 12 weeks that shows evidence of ongoing infection or malignancy.
 - a. Chest radiograph is optional for participants under 18 years of age at time of screening.

Infections or Predisposition to Infections

20. History of chronic or recurrent infectious disease, including but not limited to chronic renal infection, chronic chest infection (eg, bronchiectasis), recurrent urinary tract infection (recurrent pyelonephritis or chronic nonremitting cystitis), severe fungal infection (mucocutaneous candidiasis), or open, draining, or infected skin wounds or ulcers.
21. History of an infected joint prosthesis or has received antibiotics for a suspected infection of a joint prosthesis, if that prosthesis has not been removed or replaced.

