9.3.5. Safety Analyses

Safety data, including but not limited to, AEs, SAEs, AESIs (active TB, malignancy, possible Hy's Law cases), discontinuation of study intervention due to AEs, changes in laboratory assessments, changes in vital signs, and changes in weight, changes in PHQ-9 scores, and changes in C-SSRS

will be summarized. Treatment-emergent AEs will be summarized by treatment group and MedDRA system organ class and preferred terms. Details will be specified in the SAP.

All safety analyses will be performed using the Safety Analysis Set; participants will be summarized by the intervention they received.

Adverse Events

The verbatim terms used in the CRF by investigators to identify AEs will be coded using the MedDRA. Any AE occurring at or after the initial administration of study intervention or that is a consequence of a pre-existing condition that has worsened since baseline is considered to be treatment emergent. All reported treatment-emergent AEs will be included in the analysis. For each AE, the percentage of participants who experience at least 1 occurrence of the given event will be summarized by intervention group.

The following analyses will also be used to assess the safety of participants in the study:

- The incidence and type of AEs.
- The incidence and type of SAEs.
- The incidence and type of AESIs.
- The incidence and type of severe AEs.
- The incidence and type of treatment-related AEs and SAEs as assessed by the investigator.
- The incidence and type of AEs leading to discontinuation of study intervention.

Listings of participants with SAEs, severe AEs, AEs of psoriasis, AESIs and AEs leading to discontinuation of study intervention will also be provided. Summaries, listings, datasets, or participant narratives may be provided, as appropriate, for those participants who die, who discontinue intervention due to an AE, or who experience a severe or a SAE.

Clinical Laboratory Tests

Laboratory data will be summarized by type of laboratory tests. Selected laboratory parameters will be summarized by treatment group. Common Terminology Criteria for Adverse Events (CTCAE) and ULN will be used to identify abnormal laboratory test results, and the incidence and severity of abnormal laboratory parameters (hematology and chemistry) will be summarized by treatment group.

In addition, a listing of participants with Grade 2 or higher laboratory test results (based on the CTCAE criteria) will also be provided.

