#### **4.5.3.5. PHQ-9**

The PHQ-9 is self-administered, 9-item questionnaire measuring symptoms and severity of depression. The recall period for all items is the past 2 weeks. The items include diminished interest or pleasure, depressed mood, insomnia/hypersomnia, fatigue or loss of energy, weight loss or weight gain/appetite loss or appetite gain, feelings of worthlessness, diminished concentration/indecisiveness, psychomotor agitation/retardation, and thoughts of death/suicide. Each item is rated on a 4-point Likert scale ranging from 0 “not at all” to 3 “nearly every day”. Higher scores indicate more severe depressive symptoms. The PHQ-9 scores for depression range from 0 to 27 with higher scores indicating worse state (more severe depressive symptoms). A score of 5 to 9 is considered to be minimal symptoms of depression. A score of 10 to 14 is considered minor depression, dysthymia, or mild major depression. A score of 15 to 19 is considered to indicate moderately severe major depression, and a score  $\geq 20$  is considered to be severe major depression.

- The shift table will be provided to summarize the shift in values from baseline to postbaseline.
- A listing will be produced for all PHQ-9 score including unscheduled visits for participants with PHQ-9 score  $\geq 15$ .

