## **6.8. Appendix 8 Laboratory Toxicity Grading**

The grading scale use for lab assessments is based on ‘CCTCAE’.

If a laboratory value falls within the grading as specified below but also within the laboratory normal limits, the value is considered to be normal and will be reset to grade 0.

Pre-baseline measurements will use the same grading ranges as applied to baseline measurements. In case a test has two sets of ranges – one for baseline normal and one for baseline abnormal, the one for baseline normal will be applied for all measurements taken pre-baseline and on baseline.

Text in gray italic in the table is present in the grading scale, but is not applied by J&J when grading lab data.

CTCAE Term	Grade 1	Grade 2	Grade 3	Grade 4	J&J Implementation Notes
Blood and lymphatic system disorders					
Anemia	Hemoglobin (Hgb) <LLN - 10.0 g/dL; <LLN - 6.2 mmol/L; <LLN - 100 g/L	Hemoglobin (Hgb) <10.0 - 8.0 g/dL; <6.2 - 4.9 mmol/L; <100 - 80g/L	Hemoglobin (Hgb) <8.0 g/dL; <4.9 mmol/L; <80 g/L; transfusion indicated	Life-threatening consequences; urgent intervention indicated	Clinical signs and symptoms are not taken into consideration for grading.
Leukocytosis	-	-	>100,000/mm  ; >100 x 10  /L	Clinical manifestations of leucostasis; urgent intervention indicated	Clinical signs and symptoms are not taken into consideration for grading; Added ranges in SI unit (x 10  /L)
Investigations					
Activated partial thromboplastin time prolonged	>ULN - 1.5 x ULN	>1.5 - 2.5 x ULN	>2.5 x ULN; bleeding	-	Clinical signs and symptoms are not taken into consideration for grading.
Alanine aminotransferase increased	>ULN - 3.0 x ULN if baseline was normal; 1.5 - 3.0 x baseline if baseline was abnormal	>3.0 - 5.0 x ULN if baseline was normal; >3.0 - 5.0 x baseline if baseline was abnormal	>5.0 - 20.0 x ULN if baseline was normal; >5.0 - 20.0 x baseline if baseline was abnormal	>20.0 x ULN if baseline was normal; >20.0 x baseline if baseline was abnormal	Ranges defined for “abnormal baseline” are applied only if baseline > ULN. If baseline < LLN, then ranges for “normal baseline” are applied.

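### The laboratory table counts maximum post-baseline grade without regard to baseline grade, so for most tests unchanged pre-existing abnormalities appear as on-treatment findings; a shift table should be added

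*SAP*

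**What the plan says.** - **SAP 4.5.3.1.** The one categorical CTCAE summary is "The proportion of participants with post-baseline values by maximum toxicity grade", given overall and by age group. Participants at Grade 2 or above "will be listed". The 4-week rule limits only the end of the observation window. The section also plans a comparison of ALT and AST with the ULN, box plots of values and changes for selected measurements, and summaries of lipids and hs-CRP.
- **Protocol 9.3.5.** CTCAE grades and the ULN identify abnormal results, and "the incidence and severity of abnormal laboratory parameters (hematology and chemistry) will be summarized by treatment group". Descriptive statistics include change from baseline for selected analytes. Criteria for markedly abnormal results are left to the SAP, which defines none for laboratory tests.
- **SAP Appendix 8.** Some tests have two sets of ranges, "one for baseline normal and one for baseline abnormal". Values at or before baseline are always graded on the first set. For a participant with elevated baseline ALT or AST, post-baseline Grade 1 is "1.5 - 3.0 x baseline if baseline was abnormal". Most other rows use fixed limits or multiples of the laboratory's normal limits.
- **Other safety domains in the SAP.** Vital signs use a treatment-emergent definition, ECG abnormalities are those that differ from Week 0, anti-drug antibodies are classed as treatment-emergent or not, and C-SSRS has a shift table. For PHQ-9, "The shift table will be provided to summarize the shift in values from baseline to postbaseline".

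**The concern.** A reader of a table of maximum post-baseline grades will usually take the counts as events on treatment. For a test graded on absolute limits, someone who enters with a Grade 1 value and never changes is counted at Grade 1. For a liver enzyme graded against an abnormal baseline, the same stable participant is counted at Grade 0. One table then mixes prevalence for most tests with something close to new abnormality for a few, and nothing in it tells the reader which is which. Laboratory tests are also the exception here, because the SAP's other safety domains take baseline into account.

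At stake are the readability of a drug effect in the randomized period and the level of the rates in the later summaries, which may be quoted as rates on JNJ-77242113.

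**Working it through.** The plan states no figure on this point, so there is none to reproduce.

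**1. How many tests are affected.** Appendix 8 has 37 CTCAE rows. Eight refer to baseline: ALT, AST, ALP, bilirubin, GGT, creatinine (in part), fibrinogen and INR. The other 37 − 8 = 29 do not. Nine rows have no matching routine test in protocol Appendix 1 (aPTT, CD4, fibrinogen, haptoglobin, INR, lipase, amylase, acidosis, alkalosis), which leaves 28. Of these, six refer to baseline (ALT, AST, ALP, bilirubin, GGT, creatinine in part), and 28 − 6 = 22 do not.

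**2. Two stable participants.**
- Triglycerides 200 mg/dL at every visit, above the laboratory's normal limit: Grade 1 (150–300 mg/dL), counted.
- ALT 1.8 × ULN at every visit: 1.0 × baseline, below the 1.5 × baseline threshold, so Grade 0, not counted.

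ALP and GGT behave like ALT, with Grade 1 starting at 2.0 × baseline. Bilirubin is less clear-cut: Grade 1 starts just above 1.0 × an abnormal baseline, so small fluctuations count.

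**3. What entry criteria remove.** Exclusion criterion 17 against the Appendix 8 limits:

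| Test | Excluded at screening | Grade 2 starts |
|---|---|---|
| Hemoglobin | <10 g/dL | <10 g/dL |
| Neutrophils (10⁹/L) | <1.5 | <1.5 |
| WBC (10⁹/L) | <3.5 | <3.0 |
| Platelets (10⁹/L) | <100 | <75 |

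Grade ≥2 values for these four are therefore essentially new since screening. The whole Grade 1 range for hemoglobin and neutrophils, and part of it for WBC and platelets, can enter. Lipids, CPK, electrolytes, glucose and lymphocytes have no entry limit. For some of them Grade 2 is reached at once: potassium below the LLN is graded 2, and raised lymphocytes start at Grade 2.

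**4. Size, under assumptions.** Let *b* be the share with a pre-existing abnormality that persists, and *e* the rate of new abnormality in the rest. Neither is in the documents. Assume *e* = 5% on placebo and 10% on drug. The planned table shows *b* + (1 − *b*)*e*. A worsening-only count over all participants shows (1 − *b*)*e*.

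| *b* | Planned table | Ratio | Difference (points) | Worsening-only | Ratio | Difference (points) |
|---|---|---|---|---|---|---|
| 10% | 14.5% vs 19.0% | 1.31 | 4.5 | 4.5% vs 9.0% | 2.0 | 4.5 |
| 20% | 24.0% vs 28.0% | 1.17 | 4.0 | 4.0% vs 8.0% | 2.0 | 4.0 |
| 30% | 33.5% vs 37.0% | 1.10 | 3.5 | 3.5% vs 7.0% | 2.0 | 3.5 |
| 40% | 43.0% vs 46.0% | 1.07 | 3.0 | 3.0% vs 6.0% | 2.0 | 3.0 |

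The ratio shrinks; the difference does not change. The noise around it does. At *b* = 20% with 200 and 400 participants, the standard error of the difference is √(0.24×0.76/200 + 0.28×0.72/400) = 3.8 points in the planned table and √(0.04×0.96/200 + 0.08×0.92/400) = 1.9 points in the worsening-only count.

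Read as a single on-drug rate, as in the later summaries, 28.0% contains 20 points present before the first dose: 20/28 = 71% of the count.

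**5. Why a worsening rule cannot be applied to every test.** Entry permits ALT up to 2 × ULN. A baseline of 1.8 × ULN is Grade 1 on the baseline-normal scale. A later 3.6 × ULN is 3.6/1.8 = 2.0 × baseline, also Grade 1. The planned table counts this participant; a rule requiring a higher grade than baseline drops them, and would do so up to 3.0 × 1.8 = 5.4 × ULN. Conversely, an unchanged 1.8 × ULN would appear as a shift from Grade 1 to Grade 0.

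**The case against.** - **Nothing is biased between arms through Week 16.** This stands. Randomization balances pre-existing abnormality in expectation, no formal safety comparison is planned, and the absolute excess equals that of a worsening-only count. A reader might infer that the table hides or distorts a drug effect; the documents support only a smaller ratio and more noise.
- **The illustration is not the planned table.** This stands in part. It collapses the grades, assumes that every pre-existing abnormality persists, and uses assumed prevalence. In the real table, a move from Grade 1 to Grade 3 on an absolute-limit test appears at Grade 3. The direction still holds wherever baseline abnormalities persist.
- **Change from baseline is covered elsewhere.** Partly so. Box plots and descriptive statistics show change, and clinically relevant laboratory changes are recorded as adverse events. The displays are for selected analytes at group level and do not show who moved up a grade.
- **The protocol is not contradicted.** This stands. Incidence in protocol 9.3.5 could be read as treatment-emergent incidence, but the text does not say so.
- **The Grade ≥2 listing is sound.** Largely true for the four hematology tests in the table of entry limits, and a listing cannot dilute a rate. For tests without an entry limit, it would still list stable pre-existing values without saying so.
- **Week 52 has a control.** Only as an option: SAP 4.5 allows selected Week 24–52 analyses in re-randomized participants. The main Week 52 groups are all defined by JNJ-77242113 treatment.

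**Conclusion.** The gap is real and modest. For 22 of the 28 relevant rows, the planned table cannot separate new or worsened abnormalities from those present before dosing, while most liver tests in the same table are graded relative to an abnormal baseline. Through Week 16 the cost is a smaller ratio and extra noise. In the main Week 52 and Week 160 summaries the cost is inflated on-drug rates, by an amount that depends on baseline prevalence not given in the documents; the 10–40% range is an assumption. Grade ≥2 hemoglobin, neutrophils, WBC and platelets are little affected.

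The documents do not support the stronger conclusion that the table should be replaced by a worsening-only count for all tests. Under Appendix 8's two-scale grading, that would hide real rises in liver tests. The point is a cheap improvement in safety reporting and bears on no efficacy conclusion.

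**What to change.** In SAP 4.5.3.1:

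1. Keep the maximum-grade table, and add a shift table of baseline grade by maximum post-baseline grade, by treatment group.
2. For tests graded on absolute limits, also report the proportion whose maximum post-baseline grade exceeds the baseline grade.
3. Do not apply item 2 to ALT, AST, ALP, GGT, bilirubin or creatinine under the Appendix 8 grades. For these, either put baseline and post-baseline values on the same ULN-based scale, in the shift table as well, or footnote that the two gradings differ.
4. For placebo cross-over participants in on-drug summaries, take the last value before the first JNJ-77242113 dose as the reference, because the SAP's safety baseline (SAP 4.1) precedes placebo.
5. Show the baseline grade in the Grade ≥2 listing.

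The cost is a few lines of SAP text and one or two standard tables. Appendix 8 already grades baseline values, and no new data are needed.
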